### Inclusion Criteria

We will include pregnant women with singleton or multiple gestation between 220/7 to 316/7 weeks gestation who present with regular uterine contractions defined as at least one contraction every 10 minutes for 30 minutes with at least one of the following:

- cervical change of at least 1 cm or
- cervical dilation of 2 cm at the time of initial exam or
- positive fetal fibronectin and transvaginal cervical length <2.5 cm

These criteria were chosen since these findings are associated with acute preterm labor.

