### **Secondary Outcomes**

Secondary outcomes will include the following:

- Percentage of women achieving 7 days pregnancy prolongation
- Number of hours from first dose of tocolytic agent to delivery. The hours will be rounded to the closest day.
- Neonatal outcomes including birthweight, gender, need for NICU admission, length of NICU admission, length of hospital stay, rate of death, intraventricular hemorrhage, necrotizing enterocolitis, culture positive sepsis, neonatal seizures, need for mechanical ventilation, ECMO, CPAP or blow by oxygen and length of mechanical ventilation, CPAP, ECMO or blow by oxygen.
- Pregnancy outcomes including rate of cesarean delivery, clinical chorioamnionitis, preterm premature rupture of membranes, preeclampsia, need for blood transfusion
- Reported adverse effects including headache, nausea, vomiting, acid reflux, maternal hypotension including BP<90/60, maternal tachycardia with heart rate >120, syncope.

Neonatal outcomes will be followed until hospital discharge or day 120 of life.

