### **Data analysis and sample size calculations**

We have conducted a Bayesian power analysis for this study comparing combination therapy with nifedipine and indomethacin versus single agent therapy with nifedipine alone for treatment of acute preterm labor. Our primary outcome is the percentage of women that remain pregnant at >48 hours.

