#### **Design prior distributions:**

Single agent outcome rate: 77% (95% CI: 68%-85%)

Combination outcome rate: 95% (95% CI: 74%-99.9%)

Our clinically important absolute difference (combination % - single agent %) of > 10%. Pr(difference >10%)> level of certainty. Our enthusiastic prior is the same as the design prior above. Neutral prior assumes no difference between two groups, RR=1.0 with 95% CI of 0.5-1.33.

Level of Certainty	N per group	Bayesian Power	
		Enthusiastic prior	Neutral prior
67%	30	0.83	0.77
	40	0.85	0.80
	50	0.85	0.83
75%	100	0.86	0.83
	30	0.80	0.72
	50	0.83	0.79
80%	100	0.84	0.81
	30	0.77	0.68
	50	0.79	0.77
	100	0.84	0.80

For the primary outcome of % of women that remained pregnant > 48 hours, we assumed rates of 77% (95% Credible Interval: 68%-85%) in the nifedipine alone group and 95% (95% Credible Interval: 74%-99.9%) in the nifedipine-indomethacin group. We assumed an absolute risk difference (RD) of 10% between the two groups as the minimum clinically important treatment effect. We are interested in a posterior probability of 67% or more for this effect, i.e. Pr(RD>0.10) > 0.67. We conducted a simulation study to calculate the needed sample size to have 80% power to detect an RD >10% with 67% probability. We used the expected outcome rates to simulate data, and we assumed a neutral prior (meaning no a priori difference between the two groups with a RD centered at 0) for the final analysis. A sample size of n=40 per group will have 80% power of detecting a RD of 10% or more with 67% certainty.

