#### *Indomethacin*

Indomethacin is a category C medication. Fetal exposure to indomethacin is associated with the development of antenatal closure of the ductus arteriosus, antenatal oligohydramnios, postnatal persistent patent ductus arteriosus, necrotizing enterocolitis, intraventricular hemorrhage and postnatal renal failure as reported clinically and in studies in rodents. Many of these adverse events occur with prolonged courses of indomethacin administered for both greater than 48 hours and over 32 weeks gestation. Other potential risks include nausea/vomiting/heartburn/abdominal discomfort (3-9%) and headache (11.7%).

Although employed in clinical practice at times, combination nifedipine-indomethacin has not been studied within a randomized controlled trial. Prior studies have raised concern for combination tocolytic agents due to reported cases of pulmonary edema, myocardial infarction and cardiovascular collapse. However, these included ritodrine, magnesium and terbutaline, which as individual agents increase this pulmonary risk. Thus, these risks are minimal with our study combination regimen.

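### Durations of NICU stay, hospital stay and respiratory support have no rule for infants who die, so an arm with more early deaths will tend to look better on them

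*Combined protocol and SAP*

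**What the plan says.** Secondary Outcomes puts "length of NICU admission, length of hospital stay, rate of death" in one list of neonatal outcomes and adds "length of mechanical ventilation, CPAP, ECMO or blow by oxygen". The only further rule there is "Neonatal outcomes will be followed until hospital discharge or day 120 of life". Death is neither named as an end of follow-up nor given a value in any duration.

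Nothing elsewhere fills the gap. The analysis section (Data analysis and sample size calculations, with Design prior distributions) deals only with the primary outcome: "Our primary outcome is the percentage of women that remain pregnant at >48 hours". Methods names broad categories of data to collect. Neonatal follow up describes routine clinical care.

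Two features of the design bear on the point. Inclusion Criteria admits singleton and multiple pregnancies from 22 0/7 to 31 6/7 weeks. Under Medication regimen, indomethacin is assigned in one arm only, and the Indomethacin risk section states that "Fetal exposure to indomethacin is associated with the development of antenatal closure of the ductus arteriosus", going on to list necrotizing enterocolitis, intraventricular hemorrhage and renal failure.

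**The concern.** An infant who dies on day 3 has a 3-day hospital stay and at most 3 days on a ventilator. On a length-of-stay scale those are among the best values possible. If deaths are counted to the day of death, higher early mortality pulls the arm's mean down. If deaths are dropped, the comparison is between survivors, a group defined after randomisation.

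Some neonatal deaths should be expected with enrolment from 22 weeks, and the plan itself makes death an outcome. The rationale hopes that longer pregnancy could lead to better neonatal outcomes, so a shorter stay or fewer days of support would naturally be read as supporting the combination. The trial is open label, so leaving the treatment of deaths to be settled after the data are seen is an avoidable freedom.

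A lesser matter is the cut-off at day 120. An infant born at 22 0/7 weeks is then at 39 1/7 weeks (120 days = 17 weeks + 1 day) and could still be an inpatient. That is the earliest possible case, not a typical one.

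**Working it through.** The plan states no figure for these outcomes, so there is none to reproduce. The check is of direction and rough size.

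**Inputs from the plan.** 40 women per group (Design prior distributions), taken here as 40 independent infants per arm; day 120 as the horizon (Secondary Outcomes).

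**Assumed inputs.** Survivors' stay S = 70 days, SD 25, the same in both arms, so there is no true effect on stay. Time to death is exponential with mean D = 10 days. Mortality d is 10% versus 20%, or 10% versus 15%.

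**1. Mean stay counted to death** = (1 − d)·S + d·D.
- d = 10%: 0.90 × 70 + 0.10 × 10 = 64.0 days
- d = 15%: 0.85 × 70 + 0.15 × 10 = 61.0 days
- d = 20%: 0.80 × 70 + 0.20 × 10 = 58.0 days

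The arm with more deaths looks 6.0 days better at 10% versus 20%, and 3.0 days better at 10% versus 15%. Simulation with stays limited to 5–120 days gives 63.8 versus 57.9 days for the first pair. The sign needs only D < S, that is, deaths falling earlier than a typical discharge.

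**2. Set against sampling error.** Variance per infant = (1 − d)·25² + d·10² + d(1 − d)·(S − D)².
- d = 10%: 562.5 + 10 + 324 = 896.5
- d = 15%: 531.25 + 15 + 459 = 1005.25
- d = 20%: 500 + 20 + 576 = 1096

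SE of the difference, 10% versus 20%: √((896.5 + 1096)/40) = 7.1 days. The shift is 6.0/7.1 = 0.85 SE, so the arm with more deaths has the shorter mean in about 80% of trials. For 10% versus 15%: √((896.5 + 1005.25)/40) = 6.9 days, 3.0/6.9 = 0.44 SE, about 67% of trials. Simulation at 40 per arm agrees (80% and 67%).

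**3. Days alive and out of hospital to day 120, death scored 0** = (1 − d)·(120 − S).
- d = 10%: 0.90 × 50 = 45.0 days
- d = 15%: 0.85 × 50 = 42.5 days
- d = 20%: 0.80 × 50 = 40.0 days

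The arm with more deaths is now 5.0 days worse (10% versus 20%) or 2.5 days worse (10% versus 15%). The sign reverses.

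**4. Other assumptions.** With survivors' stay of 40–80 days and death at day 3–7, step 1 gives an apparent gain between 10 points × (40 − 7) = 3.3 days and 10 points × (80 − 3) = 7.7 days for 20% versus 10% (or 15% versus 5%). For 10% versus 5% the range is half that, 1.7 to 3.9 days.

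**5. Survivors only.** With survivors' stay of mean 60 days (SD 25) and mortality of 5% versus 10%, 5% versus 15% or 10% versus 20%, a simulation shows no shift if death is unrelated to underlying stay. If infants who would have stayed longer die more often (assumed correlation 0.5), the arm with more deaths looks 1.0 to 2.1 days better and has the shorter mean in 58–65% of trials.

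**The case against.** The plan sets no analysis for any secondary outcome, so counting stay to death is one reading, not an adopted method. On a survivors-only reading the shift may be small or absent. The outcomes are unpowered and secondary, and mortality stands in the same list, so a doubling such as 4 versus 8 deaths among 40 would be visible. The illustrated shift is smaller than one standard error. All of this stands. It limits the point to a tendency, and it makes the matter minor. It does not remove the gap: showing mortality beside a duration does not correct the duration, and the survivors-only reading gives up the randomised comparison.

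A second objection concerns the remedy. The documents do not itemise dates of death, discharge or support, and follow-up ends at discharge or day 120. A measure needing deaths or readmissions after discharge would need longer follow-up, which sits badly with the statements that enrolment asks no extra time beyond the first 48 hours and that the study needs no funding. This also stands, and the fix is framed so as not to depend on post-discharge data.

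A reader might infer three stronger things. One is that the arm with more deaths is certain to look better; at 40 per arm it does so in about 80% or 67% of trials on the assumed inputs. Another is that the combination is expected to raise mortality; the protocol lists neonatal harms linked to indomethacin but gives no mortality figure for either arm. The third is that the main conclusion is at risk; the primary outcome is continued pregnancy beyond 48 hours and does not involve these durations.

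**Conclusion.** The omission is real. No section links the durations to death, and durations taken as written treat an early death as a favourable value. The direction of the bias rests only on deaths occurring earlier than a typical discharge. Its size, about 6 days at 10% versus 20% mortality and about 3 days at 10% versus 15%, against a standard error of about 7 days, rests wholly on assumed mortality and stay and on 40 independent infants per arm. Only secondary outcomes are affected; the primary outcome and sample size are not. This is a cheap improvement of minor severity.

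**What to change.** Before analysis, define each duration so that death cannot be a good result. One sound choice, applied to every infant in the mother's randomised arm:

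- Days alive and out of NICU, and out of hospital, through day 120; and days alive and free of each form of respiratory support through day 120.
- In-hospital death before day 120 scores 0. An infant still in hospital at day 120 scores 0 out-of-hospital days.
- Infants discharged alive are counted as alive, at home and off support from discharge to day 120; those sent home on a support are not counted as off that support. Written as an explicit assumption, this needs no follow-up beyond what is planned.
- Show mortality and the components beside each measure, since death and an infant still in hospital at day 120 share the score 0.
- Report survivors' length of stay as descriptive only.
- Allow for clustering of multiples within mother.

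Ranking deaths worst, or analysing discharge alive with death as a competing event, would also close the gap.

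Cost: a few sentences of protocol or SAP text, and a check that the data form records age at death, at discharge and on each support, which the listed lengths imply but the protocol does not itemise. The downside is that the measure mixes death with morbidity and rests on the stated assumption about time after discharge.

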### **Known Potential Risks**

For this comparative effectiveness trial, there is little incremental risk as patients are receiving clinically accepted treatment regimens and the research aspect of this study is being randomized to one of these two treatment regimens vs. being assigned by treating physician. It is the practice of some physicians to use multiple tocolytic agents in tandem. There is a chance of additive maternal and fetal side effects with the two drugs being used together; however, many of the side effects are mild and reversible with the cessation of the medications. In previous trials using combination tocolytics, the risk of adverse side effects was not significantly amplified in the combination therapy group. It is unlikely that the side effects will be synergistic as the mechanisms of action of indomethacin and nifedipine differ significantly. Preliminary assessments of interaction on pharmacological engines such as the FDA and Epocrates show no known interactions between indomethacin and nifedipine.

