### **Neonatal follow up**

Neonatal follow up in the study will not differ from the follow up of neonates whose mothers received single tocolytics. Neonates receive routine follow up by the pediatrician or neonatologist if the admitted to the neonatal intensive care unit (NICU). If neonatal exam is concerning in an infant antenatally exposed to indomethacin (hypotension, cardiac murmur that does not resolve), an echocardiogram will be obtained at that point to assess the ductus arteriosus. There are no known fetal effects of nifedipine. Enrollment in the study will not incur extra time commitment for mother or baby aside from the initial 48 hours to administer tocolytic therapy.

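### Patent ductus arteriosus and neonatal renal failure, which the protocol associates with indomethacin, are not named outcomes, and the echocardiogram provision is stated only for exposed infants

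*Combined protocol and SAP*

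**What the plan says.** **Harms.** The Indomethacin subsection of Known Potential Risks opens its list with "Fetal exposure to indomethacin is associated with the development of antenatal closure of the ductus arteriosus". It goes on to antenatal oligohydramnios, "postnatal persistent patent ductus arteriosus", necrotizing enterocolitis, intraventricular hemorrhage and "postnatal renal failure". It then qualifies the list: "Many of these adverse events occur with prolonged courses of indomethacin administered for both greater than 48 hours and over 32 weeks gestation". Known Potential Risks also accepts that "There is a chance of additive maternal and fetal side effects with the two drugs being used together".

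**Outcomes.** The neonatal list under Secondary Outcomes includes "intraventricular hemorrhage, necrotizing enterocolitis, culture positive sepsis, neonatal seizures, need for mechanical ventilation", together with death, birthweight, NICU and respiratory-support items. It is introduced as an open list. On duration it says: "Neonatal outcomes will be followed until hospital discharge or day 120 of life". The Methods section adds a general statement that neonatal and fetal outcomes will be collected.

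**Work-up.** Neonatal follow up begins: "Neonatal follow up in the study will not differ from the follow up of neonates whose mothers received single tocolytics". It then says that an infant exposed to indomethacin before birth whose exam raises concern will have an echocardiogram to assess the ductus. It makes no corresponding statement for unexposed infants. Study Design describes the trial as open label.

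**The concern.** Indomethacin is the only assigned difference between the arms, and the protocol says this combination has not been tested in a randomized trial. The trial's neonatal safety data would therefore be of interest whatever the primary result. Followed as written, the plan supports a two-arm display of enterocolitis, hemorrhage and death, but it does not commit to the same display for ductal or renal harm.

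The echocardiogram provision adds a second difficulty. If ductal findings were later taken from charts, imaging might have been prompted by known exposure in one arm and left to routine judgment in the other. Without the number imaged in each arm, a reader could not separate a drug effect from a difference in who was looked at.

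**Working it through.** The plan gives no figure on this point to reproduce. The check is an item-by-item comparison of sections, followed by a short calculation of achievable precision.

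**1. Harms against outcomes**

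| Harm in the Indomethacin section | Named under Primary or Secondary Outcomes? |
|---|---|
| Antenatal ductal closure | No |
| Antenatal oligohydramnios | No |
| Persistent patent ductus arteriosus | No |
| Necrotizing enterocolitis | Yes |
| Intraventricular hemorrhage | Yes |
| Postnatal renal failure | No |

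Six harms, two named, 6 - 2 = 4 not named. The pregnancy outcomes contain no amniotic fluid item, and the listed adverse effects are all maternal.

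**2. Which of the four can be acted on**

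Patent ductus arteriosus and renal failure are neonatal diagnoses that fall within the existing follow-up to discharge or day 120. Antenatal ductal closure and oligohydramnios would need prenatal imaging. No section schedules any, and the Medication regimen section says nothing further will be done beyond the assigned drugs. The actionable gap is therefore two items.

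**3. Echocardiogram provision**

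Statements for exposed infants: 1. Statements for unexposed infants: 0. Exposure mostly follows arm, but the Rescue regimen section lets physicians give other tocolytics, so some control infants could also be exposed.

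**4. Expected frequency**

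Entry ends at 31 6/7 weeks and the course is 48 hours, so the trial sits mostly outside the region that the protocol links to many of these events. The margin is narrow: 31 weeks 6 days plus 2 days is 32 weeks 1 day, and Table 1 includes an indomethacin dose at 48 hours.

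**5. Precision if the items were added**

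The input is 40 per group (sample size section). Event counts and numbers imaged are assumptions, with one infant per woman.

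- *Difference, Newcombe interval, 4/40 against 2/40.* The Wilson 95% limits are 0.040 to 0.231 for 4/40 and 0.014 to 0.165 for 2/40. The difference is 0.10 - 0.05 = 0.05. Lower limit: 0.05 - √[(0.100 - 0.040)² + (0.165 - 0.050)²] = -0.080. Upper limit: 0.05 + √[(0.231 - 0.100)² + (0.050 - 0.014)²] = 0.185.
- *No cases among n imaged infants in an arm.* The exact two-sided 95% upper limit is 1 - 0.025^(1/n):

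| Imaged (assumed) | Upper limit |
|---|---|
| 40 | 8.8% |
| 20 | 16.8% |
| 10 | 30.8% |

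A report of no ductal cases thus means very different things depending on the number imaged. These limits show precision only, because infants imaged for a concerning exam are a selected group.

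**The case against.** The strongest reply has four parts.

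- **Open list.** The outcome list is not exhaustive and the Methods section refers to neonatal and fetal outcomes generally. This stands: a reader might infer that the plan rules out collecting ductal or renal data, and the text does not say that. What remains is that nothing commits the trial to these two items or to recording them alike in both arms.
- **Low expected frequency.** The protocol says only that exposure is associated with these harms, partly on rodent evidence, and ties many of them to longer and later courses. This also stands. It would be too strong to say that the protocol attributes the harms to the drug. Still, many is not all, and low frequency affects expected counts rather than whether to record them.
- **The echocardiogram sentence describes care, not endpoint ascertainment.** No listed endpoint depends on it. A reader might infer that unexposed infants would be refused imaging, or that detection bias has been shown. Neither is supported: the section does not restrict imaging in unexposed infants, and routine follow-up applies to all. The problem arises only if ductal findings are compared.
- **The follow-up sentence may be consistent.** The phrase about single tocolytics could cover indomethacin alone, which the background describes as a common single agent. On that reading there may be no contradiction. In this trial, however, the comparator is nifedipine alone, so the wording is at least unclear.

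Nor should the gap be widened to say that no secondary outcome is defined. Maternal hypotension and tachycardia have thresholds, and time to delivery has a rounding rule. It is the listed neonatal diagnoses that have no stated definitions.

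**Conclusion.** The point holds as a minor one. Two of the six harms that the protocol associates with fetal indomethacin exposure are named as outcomes. Of the four that are not, patent ductus arteriosus and renal failure can reasonably be added, while the two antenatal findings can only be noted where they already appear in the chart. The primary outcome and sample size are unaffected.

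Unequal ductal detection is a possibility whose size the documents do not allow anyone to estimate. The conclusion rests on two assumptions: that neonatal records contain the two diagnoses and the echocardiogram dates, which no section states, and, for the precision figures only, one infant per woman, although multiple gestations are eligible.

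**What to change.** Under Secondary Outcomes, add diagnosed or treated patent ductus arteriosus and neonatal renal failure. Abstract both with one written definition, applied identically in the two arms, from records already followed to discharge or day 120.

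Report by arm how many infants had an echocardiogram, and classify unimaged infants as not assessed, not as negative. Record antenatal ductal constriction and oligohydramnios only where charted, with the number imaged. Present everything descriptively, with intervals that allow for siblings from multiple gestations where event numbers permit.

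Reconcile the opening sentence of Neonatal follow up with the exposure-based echocardiogram sentence. No clinical rule is proposed here.

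The cost is a few chart fields, the writing of shared definitions and a little extra tabulation, with no new procedure. The limits are wide intervals at 40 per group, antenatal findings that may be largely unassessed, and imaging counts that reveal unequal detection without removing it.

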## **RESEARCH DESIGN & METHODS**

### Study Design

We propose an open label, randomized, comparative effectiveness controlled trial of nifedipine alone vs. nifedipine-indomethacin in pregnant women for the treatment of acute preterm labor. Prior studies have confirmed that tocolytic therapy can prolong pregnancy for 48 hours to achieve corticosteroid therapy in women with preterm labor. Thus, administering just a placebo for tocolysis is not justified at this time.

Consenting subjects will be randomly allocated to receive one of two clinically accepted clinical regimens, either nifedipine alone or nifedipine plus indomethacin.

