### Exclusion Criteria

We will exclude pregnant women with:

- clinical chorioamnionitis (defined as a temperature of >100.4 F and any of the following: fundal tenderness, maternal tachycardia, fetal tachycardia or purulent vaginal discharge)
- non reassuring fetal heart tones
- suspected placental abruption
- preterm premature rupture of membranes
- prior tocolytic treatment during the past 48 hours
- known adverse effect to indomethacin or nifedipine
- already receiving nifedipine for chronic hypertension

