## Randomization

Randomization will be performed based on a computer-generated list that will be created by a non-clinical member of the research team. Randomization will be stratified by site. A permuted block randomization with a random fashion will be used to prevent imbalances between groups. The medication based on the computer generated list will be typed out on a piece of paper with the medication regimen written according to the below regimens. This piece of paper will be placed in an opaque envelope and numbered according to the computer generated list. The opaque envelopes will be kept on the obstetrical unit and be managed by the research team.

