## Methods

Women will receive the first dose of either nifedipine-indomethacin or nifedipine after it is determined necessary that the patient will require medications for preterm labor by the caring physician according to clinical management for a 48 hour time period. 48 hours is chosen based on current American College of Obstetrics and Gynecology recommendations, which state that tocolytic therapy should be administered to allow for administration of antenatal corticosteroids and transfer to a tertiary facility. Antenatal steroids have been shown to accelerate fetal lung maturity as well as decrease the incidence of intraventricular hemorrhage and necrotizing enterocolitis. The optimal timing of delivery after administration of corticosteroids is at least 48 hours but less than 7 days after steroid administration. Data will also be collected regarding maternal demographics, pregnancy characteristics, medications administered, length of pregnancy, and maternal/ outcomes and neonatal fetal outcomes.

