**Rescue regimen**

If it is determined that either the nifedipine-indomethacin or nifedipine alone is not adequate or adverse effects occur during the treatment of preterm labor, then other tocolytic regimens may be administered according to the managing physicians.

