#### *Nifedipine*

Nifedipine is a category C medication and is generally well tolerated. There are no associated teratogenic abnormalities in human pregnancies. The most frequently reported side effect in pregnancy is headache (7.5-31.2%) which is associated with transient hypotension caused by loading doses. Other reported adverse effects include flushing/heat sensation (5-43.7%), dizziness/lightheadedness/giddiness (6-27%), weakness (12%), nausea (11%), muscle cramps (8%), peripheral edema (7%), nervousness/mood changes (7%), palpitations/tachycardia (7%), dyspnea (6%) and nasal congestion/sore throat (6%). Nifedipine does not appear to influence fetal movement, heart or blood flow and thus does not have any direct fetal effects. In pregnancies with multiple gestations, nifedipine has been associated with increased dyspnea.

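### Adverse effects are counted in an open-label trial with no common way of asking and no reference to the woman's state before the first dose

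*Combined protocol and SAP*

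**What the plan says.** The combined protocol and SAP, under Secondary Outcomes, lists "Reported adverse effects including headache, nausea, vomiting, acid reflux, maternal hypotension including BP<90/60, maternal tachycardia with heart rate >120, syncope". Symptoms appear by name only. The two vital-sign items are fixed limits with no reference to an earlier reading.

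Other sections bear on how this outcome will behave:

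- Study Design: "We propose an open label, randomized, comparative effectiveness controlled trial". There is no placebo for indomethacin.
- Randomization: "Randomization will be stratified by site", with permuted blocks.
- Exclusion Criteria: the only mention of maternal heart rate is within "clinical chorioamnionitis (defined as a temperature of >100.4 F and any of the following: fundal tenderness, maternal tachycardia, fetal tachycardia or purulent vaginal discharge". No criterion concerns low blood pressure.
- Methods: "Data will also be collected regarding maternal demographics, pregnancy characteristics, medications administered, length of pregnancy, and maternal/ outcomes and neonatal fetal outcomes". Vital signs and symptoms before the first dose are not named.
- Rescue regimen: if "adverse effects occur during the treatment of preterm labor, then other tocolytic regimens may be administered according to the managing physicians". The physicians who judge adverse effects therefore know the arm, and their judgement can also change the treatment received.

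No section states who asks about symptoms, whether women are prompted, how often vital signs are read for this outcome, over what period events count, or how adverse effects will be analysed.

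**The concern.** Tolerability of the pair is an open question within the protocol itself. The Indomethacin section states that no randomised trial has studied this combination. Known Potential Risks accepts that effects may add together and takes reassurance from earlier combination trials. The Background, however, cites a study of salbutamol with nifedipine in which the combination group had more adverse effects. This trial would supply the first randomised comparison for the pair, so how events are counted matters.

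Two weaknesses stand out.

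1. Headache, nausea, vomiting and reflux are subjective, and the Indomethacin section attributes such symptoms to the added drug. When everyone knows the allocation and no common procedure is set, the arms may be asked, or may volunteer, unequally. Randomisation does not protect against that.
2. An afebrile woman can enter with a heart rate above 120, and any woman can enter with a blood pressure below 90/60. Nothing in the definition stops her from counting as an event.

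**Working it through.** The plan gives no figure for the adverse-effect comparison, so there is none to reproduce. From the plan come 40 women per group (Data analysis and sample size calculations), headache 7.5% to 31.2%, nausea 11% and palpitations/tachycardia 7% (Nifedipine section). Capture probabilities, the share abnormal at entry and the size of a true effect are assumptions, shown as ranges.

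**Step 1. Unequal asking, no true difference.** Reported rate = true rate × probability of capture. With equal true rates, the relative risk is the ratio of the capture probabilities.

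- 90% against 70%: RR = 0.90/0.70 = 1.29. For headache, RD = 0.20 × 7.5% = 1.5 points to 0.20 × 31.2% = 6.2 points.
- 90% against 50%: RR = 0.90/0.50 = 1.80. For headache, RD = 0.40 × 7.5% = 3.0 points to 0.40 × 31.2% = 12.5 points.
- Nausea at 11% with 90% against 50%: 9.9% against 5.5%, or 4.0 against 2.2 women of 40.

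The better-captured arm may be either one. Swapping the arms inverts the ratio.

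**Step 2. Women past a limit at entry.** Let b be the share already past the limit, all of them assumed to count as events. Rate by fixed limit = b + (1 − b) × new-onset rate. Take new onset of 7% on nifedipine alone and an assumed doubling to 14% on the combination. Counting new onset only gives RR 2.0 and RD 7.0 points.

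| b (assumed) | Combination | Nifedipine | RR | RD = (1 − b) × 7.0 |
|---|---|---|---|---|
| 5% | 0.05 + 0.95 × 0.14 = 18.3% | 0.05 + 0.95 × 0.07 = 11.65% | 1.57 | 6.65 points |
| 10% | 0.10 + 0.90 × 0.14 = 22.6% | 0.10 + 0.90 × 0.07 = 16.3% | 1.39 | 6.3 points |
| 20% | 0.20 + 0.80 × 0.14 = 31.2% | 0.20 + 0.80 × 0.07 = 25.6% | 1.22 | 5.6 points |

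**Step 3. Chance imbalance at entry.** The expected difference in b between randomised arms is zero. Its standard deviation is √(2b(1 − b)/40), which is 4.9, 6.7 and 8.9 points at b = 5%, 10% and 20%. The exact binomial probability of a gap of at least 4 women (10 points) is 0.07, 0.19 and 0.33.

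**Step 4. Precision, for scale.** At 10% in both arms, the 95% half-width for the difference is 1.96 × √(2 × 0.10 × 0.90/40) = 13 points.

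**Step 5. Hours at risk.** Suppose counting runs to 48 hours or delivery. At the design rates of 95% and 77% still pregnant, with early deliveries spread evenly (assumed mean 24 hours), mean time is 0.95 × 48 + 0.05 × 24 = 46.8 hours against 0.77 × 48 + 0.23 × 24 = 42.5 hours, a ratio of 1.10.

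**The case against.** The case against is substantial, and much of it stands.

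- **Abnormality at entry does not favour an arm.** Allocation is random, so it adds equally in expectation. The risk difference moves little (7.0 to 6.65, 6.3 or 5.6 points) against a half-width near 13 points. This is right. What remains is dilution of the relative risk and extra noise.
- **A reader might infer that symptom rates will be inflated in the combination arm.** The documents do not support that. The word *reported* does not prove passive collection. Both arms knowingly take nifedipine, whose stated nausea rate (11%) exceeds the combined stomach-symptom rate given for indomethacin (3-9%). Direction and size are unknown, and the capture figures are illustrations.
- **A reader might infer that the list wrongly leaves out flushing, dizziness and dyspnea.** The list is open, since it says *including*. The scheduled nifedipine is also identical in both arms.
- **A reader might add entry abnormality to the 7% tachycardia rate and read 17%.** Simple addition double-counts women. With 10% abnormal at entry, the figure is 16.3%, and it describes one arm, not the comparison.
- **Longer treatment in the combination arm matters little.** The 10% rests on the hoped-for effect. The Nifedipine section also ties headache and transient hypotension to the loading doses, which Table 1 places in the first 40 minutes in both arms.
- **Measured readings and syncope are less open to reporting bias.** Knowledge of the arm acts on them mainly through how often they are measured or charted.

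None of this supplies a common way of asking or a pre-dose reference, and those are the two gaps.

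**Conclusion.** The concern holds as a minor weakness in a secondary outcome. The primary outcome and the sample size are untouched.

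For the symptoms, the comparison may be biased if knowledge of the allocation changes asking or volunteering. The spurious relative risk would be 1.29 or 1.80 under the assumed capture rates, and the plan gives no means of ruling this out.

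For blood pressure and heart rate, there is no systematic bias between arms. The fixed limits blur a real difference. If 5% to 20% of women enter past a limit and remain counted, a true doubling from 7% to 14% appears as a relative risk between 1.57 and 1.22. Chance imbalance at entry is appreciable at 40 per group. The documents do not give the share abnormal at entry; if it is close to zero, this second point has little practical effect.

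The small sample limits what can be said about tolerability in any case, and better counting will not change that.

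**What to change.** Add a short paragraph to Secondary Outcomes and one form, the same for both arms:

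- Before the first dose, record the listed symptoms, blood pressure and heart rate.
- Ask the same short symptom list and take the same readings at a few common times up to 48 hours or delivery. These can be chosen from the Table 1 times, when staff already attend. At least one should follow soon after the loading doses.
- Count only events not present before the first dose.
- State whether the blood-pressure limit means either component or both.
- Report hours at risk by arm, because this window still ends at delivery and so does not equalise follow-up.

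The cost is a short form and a few sentences, with no extra visits or women. A form at every dose time would be heavier: 11 times × 80 women = 880 forms across five hospitals, in a trial that the Cost and funding section says needs no funding. Prompting does not fully remove open-label reporting bias, but it makes the asking equal. The form should be in place before enrolment, since symptoms before the first dose cannot be recovered reliably afterwards.
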